
### **C-Methacetin**

Exalenz Bioscience Ltd. will supply a ready to use, non-radioactive isotope C-Methacetin solution for single-use oral administration (75 mg in 150 ml purified water), dispensed in thermoplastic polyester (PTE) bottles sealed with a plastic child resistant stopper. The CMethacetin solution can be administered via typical oral. C-Methacetin meets all of the

qualifications for a liver function test substrate: it is a nontoxic small molecule; is administered orally; is rapidly absorbed; and is exclusively metabolized by the liver. Furthermore, C can be easily synthesized into a key location within this molecule. No related adverse events have been reported when using this substance, including in vulnerable populations, and the compound remains stable over time. The C-Methacetin substrate is a well-known diagnostic reagent that has been described in the literature and used for over 30 years by researchers around the world. C-Methacetin is rapidly absorbed and metabolized by the hepatic mixed function oxidase, via O-demethylation. This process is carried out by hepatic cytochrome P450 enzymes that produce two products, acetaminophen and formaldehyde, which is transformed through two successive oxidative steps to CO2. Toxicology testing results in animals and other clinical information support the safe use of Methacetin in humans. Based on the acute toxicity studies in mice and rats where relatively high LD50 values of 1190mg/kg were administered, the Methacetin dose administered in human breath tests in adults of 75 mg, or approximately 1mg/kg, has a safety ratio in excess of 1000- fold (10). There have been no reports of any complications with the use of this substance in over 2500 patients tested worldwide (see IDE filing). The main metabolite of Methacetin is acetaminophen which has wide routine clinical use at much higher doses than orally administered dose of C-Methacetin of 75mg used in this study.

#### Preparation of C-Methacetin

Exalenz will provide 75 mg C-Methacetin in a 0.05% solution in 150mL purified water supplied in amber thermoplastic polyester (PET) bottles. No preparation is needed.

#### Investigational Product Handling

The Investigator and/or Research Pharmacist (if relevant) will be provided with Investigational Product Handling Guidelines that will provide details regarding the packaging and labeling requirements, receipt of investigational product, dispensing and accountability procedures, preparation instructions, storage and stability of Investigational product.

#### C-Methacetin Accountability

The Investigator is responsible for ensuring that all study substrate supplies received at the site are inventoried and accounted for throughout the study. The dispensing of study substrate to the subject must be documented in the respective accountability form. The study Investigational Product must be handled in strict accordance with the protocol and the container label and will be stored in a limited access area or in a locked cabinet under appropriate environmental conditions. Study substrate should be dispensed under the supervision of the investigator, or a qualified member of the investigational staff.

After completion of the study, the device must be returned to Exalenz Bioscience Ltd. and the study drug will be destroyed according to local regulations with written confirmation.

#### Requirements for Preparation before MBT:

- The subject should be fasting from drink and solid food for a minimum 8 hours  
Subject has not ingested acetaminophen-related medications (e.g. Tylenol) within the past 48 hours (subjects with acetaminophen intoxication may be included 24 hours after ingestion).
- Subject has not had any products containing caffeine for 24 hours.
- Subject has not taken any oral (by mouth) medications for at least 1 hour before the test.
- Subject has not to have any Tylenol or acetaminophen for 48 hours prior to the scheduled test.
- Subject has not received general anesthesia in the last 24 hours.
- Subject should not have taken within last 48 hours any of the following drugs: Acyclovir , allopurinol, carbamazepine, cimetidine, ciprofloxacin, daidzein,

(herbal) disulfiram, echinacea, enoxacin, famotidine, fluvoxamine, methoxsalen, mexiletine, montelukast, norfloxacin, phenylpropanolamine, phenytoin, propafenone, rifampin, terbinafine, ticlopidine, thiabendazole, verapamil, zileuton, as they are metabolized by CYP1A2 .

Breath is collected before and after the substrate is administered to the subject; no waiting period is required once the substrate has been administered. Breath is collected automatically via a nasal cannula for a total of 75 minutes (up to 15 minutes for baseline measurement and 60 minutes following ingestion of Methacetin). All test-specific equipment will be supplied by Exalenz

**Study Feasibility:** The Clinical Research Unit will provide essential resources for the conduct of the proposed research. Study coordinator already experienced from other studies with the Breath ID machine and protocol will be required for administration of the test. Subjects are expected to spend approximately 2 hours in the CRU for administration of MBT test.

**Study Limitations:** One major limitation to this study is the unknown ability to correlate MBT with various clinical data, specifically variables derived from cardiac catheterization, if not available. Cardiac output, which is measured by cardiac catheterization, is a determinant of hepatic blood flow and likewise, Fontan pressure can influence hepatic perfusion. Cardiac catheterizations are not routinely performed in healthy Fontan patients and any analysis using this variable represents a selection bias towards a symptomatic and potentially sicker subgroup. There is merit in adding a non-invasive test like MBT when looking at FALD/DCM patients, given the difficulty to predict liver outcome in these patients.

It is entirely possible that none of the secondary end-points will be achieved within the time period specified given the infrequency of such events and that the cohort may need to be followed for 3-5 years or longer to determine such outcomes.

**Data Banking:** Data will be stored on a password protected excel spreadsheet. Only the Investigators will have access to this password protected file. This file will be kept on the FSM Transplant Surgery server only and/or storage that is maintained on Northwestern Vault or other NU-own storage consistent with FSM policies. No subject identifiers will be included in this spreadsheet. All clinical data will be kept completely confidential and PHI will be de-identified at the earliest opportunity. All study documents will be retained on site (electronically or otherwise) for at least 2 years after the study has been formally terminated at the NU IRB. The investigator(s) will work with the department and FSM to ensure electronic data is erased and any paper documents are stored in Iron Mountain Record Retention Center.

**Provisions to Monitor the Data to Ensure the Safety of Participants:** The investigator will permit study-related monitoring, audits, and inspections by the NU IRB, government regulatory bodies, and University compliance and quality assurance groups of all study related documents.

#### Adverse Events

In this trial, any medical conditions not present prior to the initial administration of the test substrate but that emerge after the initial test substrate is administered and for 24 hours post administration are considered Adverse events (AEs). AEs encountered will be recorded, as well as Serious Adverse Events will be recorded. All study personnel are responsible for entering any and all nonserious and serious adverse events, regardless of severity or relationship to the C-Methacetin solution and device, and including updates to adverse event information. A follow up phone call will be made to all subjects approximately 24 hours post administration of test substrate.

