**Subjects:**

**Inclusion Criteria**

- Written informed consent obtained prior to any study-specific assessments
- Adults patients  $\geq 18$  years of age
- Liver disease secondary to congenital heart disease or cardiomyopathy

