### Requirements for Stopping Criteria for Administration of MBT Test

- Prior occurrence of any adverse events related to 13C-Methacetin solution and device
- Change in subject's health which makes continued participation unsafe. PI will see subject prior to administration of test.
- Subject has not fasted from solid food or drink for 8 hours
- Subject has consumed caffeine products within the past 24 hours
- Subject has not taken any oral (by mouth) medications for at least 1 hour before the test.
- Subject has not to have any Tylenol or acetaminophen for 48 hours prior to the scheduled test.
- Subject has undergone general anesthesia within the past 24 hours
- Subject has taken excluded medications within the past 48 hours. These medications include: Acyclovir, allopurinol, carbamazepine, cimetidine, ciprofloxacin, daidzein, (herbal) disulfiram, echinacea, enoxacin, famotidine, fluvoxamine, methoxsalen, mexiletine, montelukast, norfloxacin, phenylpropanolamine, phenytoin, propafenone, rifampin, terbinafine, ticlopidine, thiabendazole, verapamil, zileuton, as they are metabolized by CYP1A2.

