### Requirements for stopping the study

The study will be stopped if there is a pattern seen of adverse events related to the MBT test among the subjects. Since this is a small pilot study if adverse events related to the MBT test are seen in one subject the study will be stopped.

**Withdrawal of Participants:** Subjects who consent but wish to withdraw will be asked to write to the PI for reporting purposes.

**Risks and Alternatives:** Risk of MBT administration: To date, MBT (methacetin) that will be used in this study has not been associated with any complaints or side effects. However, they are still considered experimental and there may be unknown risks.

Women of childbearing age must demonstrate a negative urine pregnancy test in order to participate.

Loss of Confidentiality - Anytime information is collected, there is a potential risk for loss of confidentiality. Every effort will be made to keep all subject information confidential.

**Potential Benefits to Participants:** Subjects will not receive any potential benefits from this study.

**Vulnerable Population:** N/A

**Community-Based Participatory Research:** N/A

**Sharing of Results with Participants:** The data obtained will be accessible only to the study investigators. The results of the investigation will not be released to each individual patient.

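### The adverse event definition omits worsening of existing disease, so a test-related flare of the subject's own heart or liver disease need not count towards either AE-based stopping rule

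*Protocol*

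**What the plan says.** The Adverse Events section of the protocol gives the trial its own definition: "any medical conditions not present prior to the initial administration of the test substrate but that emerge after the initial test substrate is administered", with a window of 24 hours after administration. On recording it says "AEs encountered will be recorded, as well as Serious Adverse Events will be recorded", and it asks staff to enter events whatever their severity or relationship to the solution and device. SAEs are not defined separately. The section also plans a contact: "A follow up phone call will be made to all subjects approximately 24 hours post administration of test substrate".

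The Inclusion Criteria require "Liver disease secondary to congenital heart disease or cardiomyopathy". The predictor lists for both groups collect earlier heart failure admissions, large volume paracentesis, varices, GI bleeding and hepatic encephalopathy.

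Two rules are written in terms of adverse events. One is a bar on giving the test: "Prior occurrence of any adverse events related to 13C-Methacetin solution and device". The other is the study stop: "if adverse events related to the MBT test are seen in one subject the study will be stopped". A further bar on giving the test does not use the term: "Change in subject's health which makes continued participation unsafe". The Study Design text makes the one-year repeat test conditional on there being no contraindication.

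**The concern.** A definition restricted to new conditions suits subjects who enter without chronic illness. Here every subject enters with heart-related liver disease, so harm from the test could well appear as worsening of what is already there, and that is the class the definition leaves out.

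The classification has consequences because the stopping rule acts on a single subject. Whether one event is called an AE can decide whether the study continues. The Risks and Alternatives paragraph itself leaves room for harm not yet seen: "However, they are still considered experimental and there may be unknown risks". At stake are the completeness of safety recording and the operation of two safety rules. The breath-test results are not affected.

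**Working it through.** The protocol gives no AE rate or other figure to reproduce, so the main check is to trace the definition through the rules that use it.

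**Step 1: is the definition widened anywhere?** No clause in the protocol adds worsening, exacerbation or recurrence of an existing condition. The instruction to enter events whatever their severity or relationship says which AEs are entered. It does not change what an AE is.

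**Step 2: trace event types occurring within 24 hours of a test and judged test-related.**

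| Event | AE as defined? | Feeds the related-AE bar and the one-subject stop? |
|---|---|---|
| Vomiting, first-ever ascites or first-ever encephalopathy | Yes, a new condition | Yes |
| Non-serious worsening of existing heart or liver disease, nothing new | No | No |
| Serious worsening of existing disease | Unclear: SAEs are recorded but not defined | Unclear |
| New episode of something that had resolved before the first dose (for example volume overload) | Ambiguous: it can be read as not present | Ambiguous |

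The second row is the firm gap. The last two are uncertainties that the wording creates.

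**Step 3: the reference point.** The definition refers to the initial administration, but the test is repeated at one year. A condition present before dose 1 that resolves and returns within 24 hours of dose 2 is therefore measured against a status a year old. This is a small point, with the same ambiguity as the last row. A condition that first arises around visit 1 and recurs at visit 2 is not excluded by the wording.

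**Step 4: how often could it matter?** Inputs: 20 subjects (10 per group) and two tests each (Study Design); no complications in over 2500 patients (13C-Methacetin section).

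- Administrations: 20 × 2 = 40 at most.
- One-sided 95% upper bound for 0 events in 2500 patients: 1 − 0.05^(1/2500) = 0.001198, or 0.12% per patient.
- At least one related complication in 20 subjects: at most 1 − (1 − 0.001198)^20 = 0.0237, or 2.4%.
- The same with the bound applied to each of 40 administrations, which is conservative: 1 − (1 − 0.001198)^40 = 0.0468, or 4.7%.

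These bounds are for any related complication. Worsening of existing disease that is not classed as an AE would be only part of that. In the other direction, the protocol does not say how complications were defined or what kind of patients made up the 2500, so the figure may not cover such worsening. The frequency of the gap itself cannot be computed from the document.

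**The case against.** The strongest case on the other side is that the gap is narrow and partly covered by other provisions.

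- *Most acute harm would be new.* Noticeable worsening within 24 hours of a single 75 mg dose would mainly show as symptoms, and symptoms new to that subject are AEs. This stands, and it limits the gap to subjects who already have the same manifestation. A reader might infer from the inclusion criterion that all 20 subjects are equally exposed. The protocol shows only that all have pre-existing disease; it gives no count of those whose worsening would go unclassified.
- *Earlier episodes are history, not present conditions.* This stands as far as it goes. It is tempting to say that every repeat episode is excluded, but an episode that was over before dosing can fairly be called not present, so the text is ambiguous there.
- *SAEs are listed in addition to AEs.* This may capture serious worsening. The document does not support saying that serious worsening is excluded, nor does it show that it is included. Non-serious worsening has no such route.
- *Retesting can still be prevented.* This is correct. A reader might infer that a subject whose disease worsened would simply be retested. The unsafe-change-in-health criterion, with the PI seeing the subject beforehand, and the contraindication condition on visit 2 can both prevent that. Neither records an AE or stops the study.
- *Major worsening is sought as outcome data.* Aim 3 covers heart failure, ascites, transplant and death, so major events may be noted elsewhere. That route does not trigger the one-subject stop.
- *Staff would record worsening anyway.* Some might, but only by departing from the written definition, and capture would then vary between staff.

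**Conclusion.** The point holds in a limited form. As defined, a non-serious, test-related worsening of existing heart or liver disease within 24 hours is not an AE unless it appears as a new condition. It then feeds neither the related-AE bar nor the one-subject study stop. Serious worsening is unclear, and recurrence of a resolved condition is ambiguous. A final report of no AEs could not be read as covering non-serious worsening.

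The number of subjects likely to be affected is unknown and probably small. The 2.4% and 4.7% figures should not be read as the chance of a missed event: they bound a wider class and rest on an external safety record whose definitions are not given. No breath-test estimate changes. The conclusion assumes that staff apply the definition as written and that no other trial document widens it.

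The change should be made because the rule as stated misclassifies a relevant kind of harm in this population, one event can decide the study stop, and correction is cheap. This is a matter of safety classification and does not imply that harm has occurred or is expected.

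**What to change.** Redefine an AE as any new condition, or any worsening in severity or frequency of an existing one, from each substrate administration until 24 hours after it, judged against the subject's status just before that administration. State that SAEs follow the same rule. Add a question on worsening of known heart and liver symptoms to the 24-hour call. Leave both stopping rules as they are.

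The cost is protocol wording and one extra question. The PI already sees each subject before the test, which supplies the comparison point, and the call is already planned. The downside is that somewhat more AEs will be recorded, and a worsening judged related to the test could stop the study under the one-subject rule.

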### Requirements for Stopping Criteria for Administration of MBT Test

- Prior occurrence of any adverse events related to 13C-Methacetin solution and device
- Change in subject's health which makes continued participation unsafe. PI will see subject prior to administration of test.
- Subject has not fasted from solid food or drink for 8 hours
- Subject has consumed caffeine products within the past 24 hours
- Subject has not taken any oral (by mouth) medications for at least 1 hour before the test.
- Subject has not to have any Tylenol or acetaminophen for 48 hours prior to the scheduled test.
- Subject has undergone general anesthesia within the past 24 hours
- Subject has taken excluded medications within the past 48 hours. These medications include: Acyclovir, allopurinol, carbamazepine, cimetidine, ciprofloxacin, daidzein, (herbal) disulfiram, echinacea, enoxacin, famotidine, fluvoxamine, methoxsalen, mexiletine, montelukast, norfloxacin, phenylpropanolamine, phenytoin, propafenone, rifampin, terbinafine, ticlopidine, thiabendazole, verapamil, zileuton, as they are metabolized by CYP1A2.

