The aim of this project is to assess a non-invasive functional liver test in patients with the Fontan circulation or with DCM that may be used for prognostic purposes. Specifically, we aim to determine whether there are alterations in a Methacetin breath test (MBT) in the Fontan or DCM patient and if so, whether it is related to conventional tests of liver and cardiac function. The hypothesis is that the MBT parameters in the Fontan patient is abnormal as a result of alterations in liver perfusion, liver cell metabolic capability and transhepatic resistance secondary to hemodynamics unique to the Fontan as well as end-organ liver damage. Due to lack of robust biomarkers or other risk stratification schemes, we aim to determine whether there is prognostic value in hepatic MBT parameter in the Fontan patient.

**Aims** - The aims of this study are three-fold:

1. To measure MBT parameter in a cohort of patients with Congestive (Dilated) Cardiomyopathy and a group of Fontan patients and compare results to published normal controls.
2. To explore any association between MBT parameter and clinical parameters already available (both baseline values and changes in values after 12 months), including Fontan hemodynamics as assessed by either of the following tests: cardiac catheterization, echocardiography, non-invasive imaging of the liver (CT or MRI), non-invasive assessment of liver stiffness (ARFI, MRE or Fibroscan), laboratory investigations, and clinical characteristics (i.e. age of patient, time since Fontan operation, type of Fontan etc., onset of DCM) . The clinical parameters should be within 3 months of the MBT.
3. To determine whether MBT is predictive of clinical outcomes: heart failure, clinically significant ascites, and time to transplant or death.

**Research Design and Methods** **Study Design:** This is a prospective pilot cohort study in 20 patients with one group of 10 subjects with Dilated Congestive Cardiomyopathy (DCM) and one group of 10 adult subjects with Fontan. All subjects will be recruited from an adult congenital heart disease clinic in a tertiary care center. Patients enrolled in the study will be prospectively followed for 3-5 years and date of liver transplantation as well as survival status will be recorded.

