**Exclusion Criteria**

- Females of child-bearing potential that are pregnant or breastfeeding
- Participation in other interventional trials
- Pregnant or breastfeeding female
- Allergy to acetaminophen based medications

**Study-Wide Number of Participants:** We anticipate accruing 20 patients from our center.

**Study-Wide Recruitment Methods:** N/A

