**Adult Fontan Associated Liver Disease patients.**

- Age
- Age at Fontan
- Time from Fontan
- Type of Fontan (atrio-pulmonary, lateral tunnel, extracardiac, other)
- History of Fontan revision
- Underlying congenital heart disease lesion
- Systemic right ventricle or left ventricle
- NYHA functional class
- Six minute walk test
- Cyanosis (saturations <90%)
- Ejection fraction or systemic ventricular function (normal, mild, moderate, severe)
- Degree of atrioventricular regurgitation (none, mild, moderate, severe)
- Fontan pressure (mmHg), cardiac index (L/min/m^2), transhepatic gradient, end-diastolic pressure, PVR, SVR
- Cardiac medications (beta-blocker, calcium channel blockers, ACE/ARB, diuretics)
- History of hepatitis, alcoholism, large volume paracentesis, varices, GI bleed, hepatic encephalopathy
- History of heart failure (defined as admission for volume overload)
- Laboratory tests: comprehensive metabolic panel, CBC, PT/INR, NTproBNP, AFP, and troponin T
- Child-Pugh score
- MELD, MELD-Na, and MELD-XI scores
- Abdominal CT or MRI findings consistent with cirrhosis or portal hypertension
- Liver biopsy
- Fibroscan, ARFI or MR Elastography score

Other than the MBT, all testing will be obtained as part of the standard of care evaluation of heart and liver disease in patients with Fontan circulation or DCM.

**Study Timelines:** We anticipate that it will take approximately 2 years to recruit patients who are to be included in this study. Patient will follow 3-5 years.

**Study Endpoints:** The aim of this project is assess a non-invasive functional liver tests in patients with the Fontan circulation or DCM that may be used for prognostic purposes.

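### Eligibility ignores the drugs barred for 48 hours before each MBT, so a continuous user can be enrolled yet be untestable, or testable only after missing prescribed treatment

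*Protocol*

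**What the plan says.** Under Requirements for Preparation before MBT, the protocol says "Subject should not have taken within last 48 hours any of the following drugs" and gives a list that ends "terbinafine, ticlopidine, thiabendazole, verapamil, zileuton, as they are metabolized by CYP1A2". Requirements for Stopping Criteria for Administration of MBT Test repeats the rule as a reason not to give the test: "Subject has taken excluded medications within the past 48 hours". The same drugs follow, among them "mexiletine, montelukast, norfloxacin, phenylpropanolamine, phenytoin, propafenone, rifampin, terbinafine, ticlopidine, thiabendazole, verapamil, zileuton, as they are metabolized by CYP1A2". Carbamazepine and allopurinol appear earlier in both lists.

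The disease criterion for entry is "Liver disease secondary to congenital heart disease or cardiomyopathy", alongside adult age and written consent before any study-specific assessment. The only drug-related exclusion is "Allergy to acetaminophen based medications". The other exclusions concern pregnancy, breastfeeding and other interventional trials.

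Research Design and Methods sets 10 subjects with dilated cardiomyopathy and 10 with Fontan circulation. It places the first MBT at the earliest opportunity after consent and a second one a year later if nothing contraindicates it. Aim 2 is "To explore any association between MBT parameter and clinical parameters already available", and the predictor lists for both groups include "Cardiac medications (beta-blocker, calcium channel blockers, ACE/ARB, diuretics".

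**The concern.** The stopping criteria call these drugs excluded medications, but no exclusion criterion names them. Eligibility and the test-day rule were therefore written separately, and nothing joins them for a person who takes a listed drug without a break. Such a person meets every entry criterion, consents, and then fails the test-day check for as long as treatment continues.

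Two things are at stake. The first is data. The MBT is the study's only research measurement, there are 10 subjects per group, and the protocol states no replacement rule. The missing values would follow co-medication, and so probably underlying disease, and would not be a random subset. Study Limitations acknowledges selection of this kind for catheterization data but not here. The second is the participant. The preparation rule could be met by missing prescribed doses for a test from which the protocol promises subjects no benefit. Risks and Alternatives covers the MBT itself, pregnancy testing and loss of confidentiality, and does not mention interrupted treatment.

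**Working it through.** The protocol states no figure on this point, so there is none to reproduce. The check sets the sections side by side, followed by an illustration of size.

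**Following one subject through the text.** Take an adult with cardiac-origin liver disease who takes a listed drug every day.

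1. Inclusion Criteria: met. None of them concerns co-medication.
2. Exclusion Criteria: none applies. Acetaminophen allergy is the only drug item.
3. Scheduling of visit 1: as soon as possible after consent, with no drug review or lead-in described.
4. Test day: a listed drug has been taken within 48 hours, so the MBT is not given.
5. Visit 2: the same rule applies. The proviso about contraindications tolerates a missed second test, but it does not settle the first test or say how the drug is to be handled.
6. Afterwards: no section says whether the subject is rescheduled, replaced, kept without an MBT, or tested after the drug has been withheld.

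The outcome is either no MBT at either visit or an MBT obtained only after at least 48 hours off the drug.

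**Overlap with the predictor list.** Verapamil is the only calcium channel blocker on the barred list. Users of other agents in the class can be tested. The variable is affected only through verapamil users, who contribute an MBT only when off the drug. How their exposure would then be coded is not stated.

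**Size, for illustration.** Inputs from Research Design and Methods: 20 subjects, 10 per group, two tests each, so 20 × 2 = 40 planned tests. The share p of enrolled subjects taking a listed drug continuously is not in the protocol and is assumed to lie between 5% and 20%. Expected subjects affected = 20p. Tests affected = 40p if both visits are affected. The chance of at least one affected subject among n is 1 − (1 − p)^n.

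| p (assumed) | Subjects of 20 | Tests of 40 | At least one in a group of 10 | At least one in 20 |
|---|---|---|---|---|
| 5% | 1 | 2 | 40% | 64% |
| 10% | 2 | 4 | 65% | 88% |
| 20% | 4 | 8 | 89% | 99% |

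For the precision of a group mean, SE = s/√n. With s unchanged and m of 10 subjects tested, the ratio of standard errors is √(10/m):

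- one subject lost: √(10/9) = 1.054, about 5% wider;
- two subjects lost: √(10/8) = 1.118, about 12% wider.

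Both ratios assume that untested subjects are not replaced.

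**The case against.** The strongest reply is that this is a gap and not a contradiction. Preparation rules such as fasting and caffeine belong to the test day and need not be repeated as exclusions. The two drug lists agree with each other, and the consequence is stated: the test is not given. Some listed drugs, such as acyclovir and ciprofloxacin, are typically short courses, for which rescheduling is enough. How subjects without an MBT are analysed may be left to a statistical analysis plan. The protocol gives no prevalence, states no precision target that would be missed, and neither provides for nor forbids replacement.

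Much of this stands. A 48-hour restriction before a CYP1A2-dependent test is not an error in itself, and the size of the effect is unknown. But fasting or abstaining from caffeine is open to any subject on the day, whereas a continuous user of a listed drug cannot comply under current treatment, and rescheduling does not help. Who may enter, and what happens to prescribed drugs, are protocol matters and not analysis detail.

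Three stronger readings are tempting and are not supported:

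- A reader might infer that the protocol directs subjects to stop cardiac drugs. It gives no such direction; interruption is one of two possible ways the rule plays out.
- A reader might see a conflict with the statement that everything apart from the MBT is standard of care. That sentence concerns testing, not medication.
- A reader might conclude that the calcium-channel-blocker predictor is unusable. Only verapamil is barred, and the aim is explicitly exploratory.

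**Conclusion.** The point holds in limited form. The eligibility criteria and the test-day drug rule, each followed as written, allow a continuous user of a listed drug to occupy one of 20 places and then either give no MBT or be tested only after missing prescribed treatment. The protocol does not choose between these outcomes and does not list the second among the risks.

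That drugs such as verapamil, propafenone, mexiletine, phenytoin and carbamazepine are generally taken continuously is general knowledge, not a statement of the protocol, and no section says how often this cohort uses them. On an assumed 5-20%, 1-4 of 20 subjects are affected. The 5% and 12% losses of precision illustrate one or two untested subjects in a group of 10 and are not predictions. The calcium-channel-blocker variable is affected in part, through verapamil alone. The change is worth making because it is cheap and each untested subject removes a tenth of a group's MBT data.

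**What to change.** Reconcile Inclusion Criteria and Exclusion Criteria with Requirements for Preparation before MBT and Requirements for Stopping Criteria for Administration of MBT Test:

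1. Check current use of a listed drug at screening, before a subject takes one of the 20 places. Keep the check consistent with the inclusion criterion that written consent precedes any study-specific assessment.
2. State how an enrolled subject who takes a listed drug, including one who starts it between visits, is handled and reported. Whether treatment interruption is contemplated must be settled in the text, and Risks and Alternatives must agree with the answer. This review takes no view on whether any drug should be held or continued.
3. Record each listed drug and the time of its last dose at each MBT, so that verapamil exposure is coded as it was at the test.

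The cost is a short protocol amendment and one extra case-report-form item. The downside is slightly narrower eligibility or slower accrual.
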